Appendix 4: CYP3A4 Substrates

Examples of CYP3A4 substrates are provided below. For most up-to-date information on CYP3A4 substrates, please check the Drug Interactions Flockhart Table™ <https://drug-interactions.medicine.iu.edu/Main-Table.aspx>.

University of Indiana CYP3A4, 5, 7 P450 Drug Interactions Abbreviated "Clinically Relevant" Table of Substrates

Macrolide antibiotics:	HIV Antivirals:	HMG CoA Reductase Inhibitors:
clarithromycin	indinavir	atorvastatin
erythromycin (not 3A5)	ritonavir	lovastatin
NOT azithromycin	saquinavir	NOT pravastatin
telithromycin	nevirapine	NOT rosuvastatin
		simvastatin
Anti-arrhythmics:	Prokinetics:	
quinidine→3-OH	cisapride	Others:
		alfentanyl
Benzodiazepines:	Antihistamines:	aripiprazole
alprazolam	astemizole	boceprevir
diazepam→3OH	chlorpheniramine	buspirone
midazolam	terfenadine	carbamazepine
triazolam	Calcium Channel Blockers:	gleevec
	amlodipine	haloperidol
Immune Modulators:	diltiazem	pimozide
cyclosporine	felodipine	quinine
tacrolimus (FK506)	nifedipine	tamoxifen
sirolimus	nisoldipine	telaprevir
	nitrendipine	trazodone
PDE-5 Inhibitors:	verapamil	vincristine
sildenafil		diergotamine & ergotamine
tadalafil		fentanyl
ildenafil		

Flockhart DA. Drug Interactions: Cytochrome P450 Drug Interaction Table. Indiana University School of Medicine (2007). "/clinpharm/ddis/clinical-table/" Accessed 20 October 2016.

Appendix 5: Modified International Working Group Response Criteria in Acute Myeloid Leukemia (Cheson, 2003, Döhner, 2017)

IWG Response Criteria in AML		Bone Marrow Blasts/Myeloblast	Circulating or Peripheral Blood Blasts ^a	Absolute Neutrophil Count	Platelet Count	EMD
Morphologic Complete Remission	CR	<5% and no myeloblasts with Auer rods	None	$\geq 1.0 \times 10^9/L$ or $\geq 1,000/\mu L$	$\geq 100 \times 10^9/L$ or $\geq 100,000/\mu L$	None
CR with Incomplete Blood Count Recovery	CRi	<5% and no myeloblasts with Auer rods	None	$<1.0 \times 10^9/L$ or $<1,000/\mu L$	$<100 \times 10^9/L$ or $<100,000/\mu L$	None
Morphologic leukemia-free state	MLFS	<5% and no myeloblasts with Auer rods ^b	No hematologic recovery required			None
Partial Remission	PR	Decrease of myeloblasts % to 5% to 25% and decrease of pretreatment myeloblast % by at least 50%	All hematologic criteria of CR			
Unchanged	UN	Absence of CR, CRi or PR and criteria for PD not met				

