Partial Remission (PR)	All CR criteria met if abnormal before treatment except for: 
 • Myeloblasts decrease by 50% or more over pretreatment value but still >5%, or • Less advanced FAB or IPPS category compared to pretreatment value 	Hematologic improvement	Absolute values must last at least 6 weeks.
Marrow CR	≤5% myeloblasts and decrease by ≥50% over pretreatment value	If hematologic improved, these should be noted in addition to marrow CR (see Category B).	
Stable Disease (SD)	Failure to achieve at least PR, but no evidence of PD for at least 3 treatment cycles.		
Progressive Disease (PD)	
 • For patients with less than 5% myeloblasts: a 50% or more increase in myeloblasts to more than 5% myeloblasts. • For patients with 5% to 10% myeloblasts: a 50% or more increase to more than 10% myeloblasts. 	Myeloblast increase plus at least one of the following: 
 • ≥50% decrease in ANC or platelets • Reduction in Hb by ≥2g/dL • Transfusion dependence. 	Death during treatment

	
 For patients with 10% to 20% myeloblasts: a 50% or more increase to more than 20% myeloblasts. For patients with 20% to 30% myeloblasts: a 50% or more increase to more than 30% myeloblasts. 		
Relapse after CR or PR	
Relapse is characterized by at least one of the following:
 
 Return to pretreatment myeloblasts percentage ≥50% decrease in ANC or platelets 
Reduction in Hb by ≥2g/dL or transfusion dependence.
		
Disease transformation	
Transformation to AML (30% or more blasts).
		
Category B: Hematologic Improvement (HI)			
	Hematopoietic Lineage	Response Criteria	Definition ^a
	Erythroid (HI-E)	Major response	For patients with pretreatment Hb<11 g/dL, greater than 2 g/dL increase in Hb; for RBC transfusion-dependent patients, transfusion independence.
		Minor response	For patients with pretreatment Hb <11 g/dL, 1 to 2 g/dL increase in Hb; for RBC transfusion-dependent patients, 50% decrease in transfusion requirements.
	Platelet (HI-P)	Major response	For patients with pretreatment PLT counts of <100 x 10 ⁹ /L or 100,000/µL, an absolute increase of 30 x 10 ⁹ /L or 30,000/µL or more; for PLT transfusion-dependent patients, stabilization of PLT counts and PLT transfusion independence.

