## Relapse Free Survival [RFS]

Relapse free survival [RFS]: defined as the months from the date of response until the date of relapse as confirmed by blast counts assessment (date of the disease progression will be used since disease progression is based in blast count assessment) .

Relapse Free Survival is defined only for subjects with a best objective response of CR/CRI/CRp/PR for AML patients or CR, PR, MR, PMR for MDS patients. Subjects who do not achieve CR/CRI/CRp/PR will be excluded from this analysis.

Duration of RFS is calculated as (days):

- Date of disease relapse, patient death, or censoring - Date of first Response evaluation + 1.
- Subjects without an objective disease relapse who die for any reason will be considered to have an event on the date of death. Otherwise subjects will be censored at the date of last objective response assessment showing no relapse has occurred.

Reason for censoring	Rule
Early death	Date of death
Disease progression leading to discontinuation	Date of last OR with no relapse
New anticancer treatment started before documentation of disease progression or death	Date of last radiological assessment prior to the start of non-protocol anticancer treatment

RFS will be summarized with (Mean (SD), median, min and max).

RFS will be presented graphically using Kaplan-Meier method.

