## 6.7 Appendix

### 6.7.1 Definitions of End Points for Clinical Trials in AML by Cheson & all 2003.

Outcome	Response Category	Point of Measurement	Definition
Overall survival	All patients	Entry onto trial	Death from any cause
Relapse-free survival	CR	Leukemia-free state	Disease relapse or patient death from any cause
NOTE. Complete blood counts should be evaluated at least monthly, or more often if clinically indicated, to establish the durability of responses.			
Abbreviations: AML, acute myelogenous leukemia; CR, complete remission.

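### SAP 5.7 counts AML partial remissions in Relapse Free Survival against the SAP's own definition in 6.7.1, and contradicts itself on which MDS responders belong

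*SAP*

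**What the plan says.** The protocol lists Relapse Free Survival as an efficacy endpoint for AML and MDS (section 8.2.2) but gives it no population, start date or event. The definition comes from the SAP, in two places.

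- **SAP 5.7, who is included.** RFS is "defined only for subjects with a best objective response of CR/CRI/CRp/PR for AML patients or CR, PR, MR, PMR for MDS patients". The next sentence reads "Subjects who do not achieve CR/CRI/CRp/PR will be excluded from this analysis".
- **SAP 5.7, the clock.** Duration is "Date of disease relapse, patient death, or censoring - Date of first Response evaluation + 1".
- **SAP 5.7, the event.** For relapse, the "date of the disease progression will be used since disease progression is based in blast count assessment". Death from any cause without relapse is also an event.
- **SAP 6.7.1.** This appendix table of AML endpoint definitions gives RFS the response category CR, the point of measurement "Leukemia-free state" and the event "Disease relapse or patient death from any cause".

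The response categories are in the protocol. For AML PR, the marrow column of Appendix 5 begins "Decrease of myeloblasts % to 5% to 25% and decrease of pretreatment myeloblast % by at least 50" (per cent). For MDS, Appendix 6 has a row headed "Relapse after CR or PR".

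The SAP plans an RFS summary table (14.2.2.1), a Kaplan-Meier figure (14.2.2.1.1) and a listing (16.2.6.2). Neither the table nor the figure is planned with a split by depth of response.

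**The concern.** RFS is normally read as time in remission. If the set includes patients who were never in remission, the curve shows time from any response to progression or death, which is a duration of response under another name. A reader who takes the SAP's appendix as the definition would misread the table and figure. For MDS the problem is more basic: two programmers following adjacent sentences of 5.7 would build different analysis sets.

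**Working it through.** The documents give no RFS median, event count or sample size, so there is no stated figure to reproduce. The check is a comparison of texts, followed by arithmetic on size.

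**1. AML: who is in.** SAP 5.7 has CR, CRi, CRp and PR; SAP 6.7.1 has CR. PR is the clear conflict. Read strictly, 6.7.1 also leaves out CRi and CRp. CRh counts as a response for ORR in 5.7 but is in neither RFS list.

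**2. AML: why PR does not fit.** Appendix 5 requires under 5% marrow blasts for CR, CRi and the morphologic leukemia-free state. PR leaves 5% to 25%. A PR patient therefore never reaches the state from which 6.7.1 starts the clock. Because 5.7 takes the progression date as the relapse date, that patient's event is PD, which Appendix 5 measures as a rise of more than 50% over the pretreatment value. For example, with an assumed pretreatment 40% and PR at 20%, the marrow criterion is met only above 40% × 1.5 = 60%. That is growth beyond the original disease, not loss of a remission.

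**3. AML: start date.** A patient with PR first and CR later is timed from the PR. Protocol 13.4 puts mandatory assessments at Cycle 2 Day 1, Cycle 4 Day 1 and then every 3 cycles, with 21-day cycles. Ignoring visit windows and optional assessments:

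- PR at Cycle 2, CR at Cycle 4: 2 × 21 = 42 days before CR counted as relapse-free.
- PR at Cycle 4, CR at Cycle 7: 3 × 21 = 63 days.

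**4. MDS: who is in.** The first sentence of 5.7 admits CR, PR, MR and PMR. The second excludes anyone without CR, CRi, CRp or PR, which removes MR and PMR. Appendix 6 defines relapse only after CR or PR. PMR is not an Appendix 6 category; MR looks like its Marrow CR, but that is an inference. PR in MDS RFS is supported by Appendix 6.

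**5. How many patients.** Expected responders = n × ORR, with the anticipated ORR of 20% and the cohort sizes in SAP 4.9: 14 × 0.20 = 2.8 in B1 to B4, and 20 × 0.20 = 4.0 in B5. The PR share among responders is not given, so it is varied. Expected AML patients without PR = n × 0.20 × (1 − share); the chance of having none = (1 − 0.20 × (1 − share))^n.

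| PR share (assumed) | n = 14: expected | n = 14: chance of none | n = 20: expected | n = 20: chance of none |
|---|---|---|---|---|
| 25% | 2.1 | 0.10 | 3.0 | 0.04 |
| 50% | 1.4 | 0.23 | 2.0 | 0.12 |
| 75% | 0.7 | 0.49 | 1.0 | 0.36 |

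With so few responders, one or two PR patients can set the RFS median.

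**6. Illustration of the mixing.** Assume exponential durations with median 8 months in complete-remission responders and m months in PR, and a PR share w. The pooled median t solves (1 − w) × 0.5^(t/8) + w × 0.5^(t/m) = 0.5.

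| w | m = 2 | m = 4 |
|---|---|---|
| 25% | 5.6 | 6.7 |
| 50% | 3.7 | 5.6 |
| 75% | 2.6 | 4.7 |

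The unmixed value is 8. The durations, the shares and the premise that PR is shorter are all assumptions. These are large-sample medians, not forecasts for a set of three or four patients.

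**The case against.** The strongest reply is that 5.7 is the operative text, states its AML responder list openly, and feeds an endpoint on which nothing formal depends. The only hypothesis test is on ORR, the protocol calls all efficacy analysis exploratory (16.5.2), and RFS has no power or decision rule. With a handful of responders, the patient-level listings of response (16.2.6.1.1) and RFS (16.2.6.2) would let a reader separate CR from PR. Restricting the set also leaves so few patients that neither version gives a usable cohort median. All of this stands and limits the importance of the point. It does not remove the conflict, because nothing in the SAP says that 5.7 overrides 6.7.1.

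Three stronger readings are tempting and are not supported:

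- *That 6.7.1 also rules out MR and PMR.* It is headed for AML only, and these are MDS categories. Nor does 5.7 settle that they are included; it says both things.
- *That the CR:PR mix will distort comparisons between cohorts.* SAP 5.1 states that dose levels and treatment groups will not be compared statistically.
- *That SAP 5.14 should have declared the change.* That section lists departures from the protocol, and the protocol never defines an RFS population. The AML conflict lies within the SAP.

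**Conclusion.** Wrong as written. For AML, following 5.7 gives a curve that is not the RFS defined in 6.7.1, both in who is counted and in when the clock starts. For MDS, the analysis set cannot be determined from 5.7. These conclusions rest on the text alone.

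The size is modest: the effect is confined to the meaning of one descriptive endpoint in cohorts expected to yield about 3 to 4 responders. The 42- and 63-day shifts follow from the mandatory schedule and apply only to patients who improve from PR to CR between scheduled assessments. The documents give neither the direction nor the size of the effect on the median; the mixture figures show only what assumed durations would do.

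**What to change.** In SAP 5.7:

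1. Restrict AML RFS to named complete-remission categories. State whether CRi, CRp and CRh count, and align 6.7.1 with that choice.
2. Start the AML clock at the first assessment documenting one of the named categories. Tying it to the category avoids starting at a morphologic leukemia-free state, which is not on the SAP's responder list.
3. Give MDS its own RFS set of CR or PR, as in the Appendix 6 relapse row, and delete the conflicting exclusion sentence.
4. Report time from first response to progression or death in all responders, including AML PR and MDS MR and PMR, as a separate endpoint named 'duration of response'.

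The cost is SAP wording, one more table and one more figure. The downside is that about 1 to 3 patients per cohort would contribute to RFS, and some cohorts may have none, so individual durations would be more informative than a median. No patient's data are lost, since those leaving RFS appear under duration of response.

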**Table 1: Operating Characteristics of the 3+3 Study Design**

True but Unknown Rate of DLT (%)	Probability of Escalation (%)
20	71
30	49
40	31
50	17
60	8

The total sample size of Part A depends upon whether DLT(s) is experienced at a given dose level (i.e. whether 3 or 6 patients have been treated) and how many dose levels are tested in order to reach the MTD. A minimum of 6-10 patients will be treated at the MTD.

The sample size of up to 14 evaluable patients for Parts B1, B2, B3 and B4 and up to 20 evaluable patients in Part B5 in this study has been calculated on the basis of the following assumptions for a one-sided, within-group test of proportions, comparing an anticipated ORR of >20% against the null hypothesis rate of 5%, with power 80% for a test of size 0.2. This

calculation is based on statistical significance at the 0.2 level, since this will be taken as evidence of a trend worthy of further study. Although this is offered as a formal sample size calculation, it is acknowledged that for this early-stage study the analyses will be exploratory in nature, and that no account has been taken of multiplicity inherent in the assessment of several, presumably non-independent criteria, for ORR.

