## 5.7 Efficacy Analysis

The endpoints to be analysed in the efficacy analysis are:

**Objective response rate [ORR]** : Proportion of patients with a best objective response such as, CR (Complete Remission), Cri (Complete Remission with Incomplete hematologic Recovery), CRp (Complete Remission with Incomplete Platelet Recovery), CRh and PR(Partial Remission) for AML patients and CR, PR, MR(Marrow Response), PMR(Partial Marrow Response) for MDS patients;

CRh is defined as, CR (<5% myeloblasts and 0% blasts in the peripheral blood) with partial hematologic recovery, defined as meeting CR criteria but with ANC > 0.5 10^9/L and platelets > 50 10^9/L responses for patients with AML.

Best Objective Response (BOR) = Best response obtain during the study participation for a patient;

**Disease control Rate (Objective Response + SD) [DCR]**: Proportion of patients with a best objective response such as, CR, CRi, CRp, CRh and PR for AML patients and CR, PR, MR, PMR for MDS patients, + SD (stable disease) as an estimate of clinical benefit;

The ORR will be summarized by;

- Age group (<75 years, >= 75);
- AML Disease Cytogenetic Profile (Favourable, Intermediate, Adverse and not done);

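### SAP 5.7 counts CRh as an AML objective response but omits it from the list that qualifies for RFS, so a patient whose best response is coded CRh is in ORR and out of RFS

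*SAP*

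**What the plan says.** **ORR and DCR.** SAP 5.7 includes CRh in the AML responder list for ORR, which ends "CRp (Complete Remission with Incomplete Platelet Recovery), CRh and PR(Partial Remission) for AML patients". It does so again for DCR: "best objective response such as, CR, CRi, CRp, CRh and PR for AML patients", plus stable disease. It describes the category this way: "CRh is defined as, CR (<5% myeloblasts and 0% blasts in the peripheral blood) with partial hematologic recovery", with ANC above 0.5 and platelets above 50 (× 10⁹/L).

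**RFS.** Under the RFS heading in the same section, the eligible set is narrower: "Relapse Free Survival is defined only for subjects with a best objective response of CR/CRI/CRp/PR for AML patients". For MDS, the same sentence admits CR, PR, MR and PMR. The next sentence reads "Subjects who do not achieve CR/CRI/CRp/PR will be excluded from this analysis".

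**Best response.** The only rule is "Best Objective Response (BOR) = Best response obtain during the study participation for a patient". No order is given for CRh, CRi and CRp.

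**Elsewhere.** SAP 6.7.1 reproduces a published definition of RFS in which the response category is CR alone and the event is "Disease relapse or patient death from any cause". SAP 5.14, which lists changes from the protocol, does not mention CRh or the RFS set. Protocol Appendix 5, which investigators use to assess AML response, has rows for CR, CRi, MLFS, PR, unchanged and PD, but none for CRh or CRp.

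**The concern.** RFS should show how long the responses counted in ORR last. If one response category is in the ORR numerator but barred from RFS, the two results describe different patients. The omission is also hard to defend on disease grounds. CRh requires under 5% marrow myeloblasts and no blood blasts, whereas PR under Appendix 5 leaves 5% to 25% marrow blasts, although with full count recovery. PR is kept and CRh is not.

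The categories also overlap, so two programmers could place the same patient differently and both follow the SAP. RFS is a named endpoint with its own Part B table and Kaplan-Meier figure, and each cohort will have few responders.

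**Working it through.** The plan states no figure on this point, so the check compares the lists and then asks how much one patient matters.

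**1. Compare the AML lists in SAP 5.7.**

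- ORR and DCR responders: {CR, CRi, CRp, CRh, PR}
- RFS qualifiers: {CR, CRi, CRp, PR}
- Difference: {CRh}

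**2. See which labels fit.** The illustrative records below have 2% marrow blasts, no blood blasts and no extramedullary disease. The CRi row of Appendix 5 shows ANC <1.0 and platelets <100 in separate columns and does not say whether both are needed.

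| ANC | Platelets | Labels that fit | In RFS? |
|---|---|---|---|
| 0.7 | 70 | CRi, CRh | Yes if coded CRi, no if coded CRh |
| 1.2 | 70 | CRp (by its name), CRh; also CRi if either count suffices | Yes if coded CRp or CRi, no if coded CRh |
| 0.7 | 120 | CRh; also CRi if either count suffices | No if CRi needs both counts low; otherwise depends on the code |

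**3. Compare the two RFS sentences.** One turns on the best response, the other on whether a listed response was achieved. Take a patient who moves from CRi (ANC 0.3, platelets 30) to CRh (ANC 0.7, platelets 70). The patient achieved CRi, so the exclusion sentence does not remove them. If CRh is ranked as best, the first sentence does, and the patient leaves RFS by improving.

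**4. Read the exclusion sentence for MDS.** It is not limited to AML. Taken literally, it removes MDS patients with MR or PMR, whom the sentence before it includes.

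**5. Scale.** SAP 4.9 plans "up to 14 evaluable patients for Parts B1, B2, B3 and B4 and up to 20 evaluable patients in Part B5" and anticipates an ORR of 20%. As a check on those inputs, 14 patients with at least 2 responders required gives exact power 1 − 0.8¹⁴ − 14 × 0.2 × 0.8¹³ = 0.802, which agrees with the stated 80%.

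- Expected responders: 14 × 0.20 = 2.8 (B1, B2 or B3; B4 is MDS) and 20 × 0.20 = 4.0 (B5).
- One lost patient: 1/2.8 = 36% and 1/4 = 25% of the expected RFS set.

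The documents give no CRh share. Let *s* be the assumed share of responders whose best response is coded CRh. The expected loss is 0.20 × *n* × *s*, and the chance of losing at least one patient is 1 − (1 − 0.20*s*)ⁿ.

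| *s* (assumed) | Expected loss, n = 14 | Chance of ≥1, n = 14 | Expected loss, n = 20 | Chance of ≥1, n = 20 |
|---|---|---|---|---|
| 0 | 0 | 0% | 0 | 0% |
| 10% | 0.28 | 25% | 0.40 | 33% |
| 20% | 0.56 | 44% | 0.80 | 56% |
| 1/3 | 0.93 | 62% | 1.33 | 75% |

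**The case against.** The strongest reply is that the loss may never occur. Investigators assess by Appendix 5, which has no CRh row, so a patient with cleared blasts and incomplete counts may simply be recorded as CRi and enter RFS. If either low count suffices for CRi, every CRh patient short of full CR also meets CRi. The exclusion sentence speaks of subjects who do not achieve a listed response, and such patients arguably did. This stands as a limit on the finding: the loss arises only when CRh is assigned as best response. It does not remove the finding, because the SAP lists CRh as a response of its own and the other RFS sentence turns on the best response.

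A second reply is that SAP 6.7.1 gives CR alone, so RFS was never meant to match ORR. It is true that 6.7.1 does not bring CRh in. But SAP 5.7 already departs from it by admitting CRi, CRp and PR, so it cannot explain why CRh alone is left out.

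A third is weight. Protocol 16.5.2 treats all efficacy analysis as essentially exploratory, RFS has no test or decision rule, and listings will show response and RFS by patient. This stands, and it limits the consequence to a descriptive summary and curve.

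**Conclusion.** The omission holds as a matter of text: CRh is in the AML list for ORR and DCR, absent from the list for RFS, and no reason is given. A patient whose best response is coded CRh is counted in ORR and left out of RFS. Where CRh overlaps CRi or CRp, membership can follow the label.

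The size cannot be fixed from the documents. It rests on the design ORR of 20% and on an unknown CRh share, which may be zero. What can be said is that one lost patient is about a quarter to a third of a cohort's expected RFS set. No alpha, power or ORR figure changes.

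Three stronger readings are tempting and are not supported:

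- A reader might infer that all AML remissions with partial count recovery are dropped from RFS. Most also fit CRi or CRp, so this depends on coding.
- A reader might apply the arithmetic to B2 and B5 pooled (14 + 20 = 34). SAP 5.1 names ORR among its examples of pooled outputs but does not name RFS.
- A reader might infer that a particular order, such as CRh above CRi and CRp, is required. The documents give none.

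**What to change.** 1. In SAP 5.7, define the RFS set as every patient with an objective response as defined for ORR: CR, CRi, CRp, CRh or PR for AML; CR, PR, MR or PMR for MDS.
2. Reword the exclusion sentence to: subjects without an objective response as defined for ORR. It then no longer removes CRh patients, or MDS patients with MR or PMR.
3. Align the CR-only row in SAP 6.7.1, or annotate it as the published definition from which SAP 5.7 departs.
4. State one best-response ranking for CRh, CRi and CRp, and how CRh and CRp are derived given that Appendix 5 has neither. Once step 1 is made, the ranking affects only the category displayed, not RFS membership.

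If the sponsor means to leave CRh out of RFS, the SAP should say why, and the ranking in step 4 then becomes essential.

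The cost is a few sentences in the SAP and the matching derivation. The counts and blast percentages are already collected, so no new data are needed.

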9.3.2. Treatment

Eligible patients will visit the study site to receive study treatment and protocol-specified procedures according to the relevant Schedule of Events table in Section 11. The treatment period will consist of continuous 21-day treatment cycles of bemcentinib.

Patients will be intensively monitored throughout Day 1 to Day 4 inclusive of Cycle 1, and in addition will attend the clinic on Day 8, and Day 15. Patients will attend the clinic once per week during Cycle 2 and then once per cycle thereafter. All patients will continue to receive bemcentinib or the combination for as long as, in the opinion of the investigator, they continue to derive clinical benefit. When there is unacceptable toxicity, confirmed disease progression in the absence of clinical benefit, or withdrawal of consent, bemcentinib or combination treatment must be discontinued. For patients in the combination arms (Part B2, B3 or B5), if treatment related toxicity requires permanent discontinuation, and the toxicity can be clearly assigned to one of the study treatments, the other study drug in the combination can be continued if it is safe to do so (investigator discretion) in the absence of disease progression or intolerable toxicity. The investigator may also decide to discontinue both study treatments at this time.

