12.4. Continuation of Treatment

It is acknowledged that the R/R AML setting is a high unmet need for effective therapies, more so for those elderly patients unsuitable for intensive chemotherapy enrolled into this study. Unlike intensive chemotherapy approaches where a clinical response may be observed relatively early in the treatment phase, the Sponsor has observed clinical responses occurring later in patients treated with bemcentinib in its immunotherapeutic mode of action when given as monotherapy or in combination with other agents. Given that AXL mediates multiple survival mechanisms used by cancers (chemotherapy drug resistance, immune evasion) and given AXL is found at high levels on immune cells in proximity to some tumors and on the tumor cells themselves, it is not unexpected that it may take longer to observe some clinical responses in some patients as bemcentinib inhibits the expression of AXL and allows the body's own immune system to kill tumor cells. This would explain both the early (cytotoxic like consequences of reversal of EMT) and the late (activation of innate immune anti-tumor responses) responses which have been observed in this study. Therefore, it is recommended that study treatment is administered for at least 3 cycles as the time-to-response may be delayed. Patients will continue to receive study treatment for as long as, in the opinion of the investigator, they continue to derive clinical benefit.

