13.4. Clinical Efficacy Assessments

All patients must undergo baseline disease assessments at Screening (peripheral blood and BM). Response assessments will be performed at Cycle 2 Day 1 (pre-dose), Cycle 4 Day 1 and then repeated after every 3 cycles or when clinically indicated. Patients that complete 12 months on study treatment, and have not experienced PD, will undergo response assessment every 5 cycles until PD is confirmed. A BM assessment may be performed at any time during the study as clinically indicated as outlined in the relevant Schedule of Events (Tables 4-6) in Section 11. Response assessment will be performed by the investigator according to the modified IWG response criteria for AML (Cheson, 2003 and Döhner, 2017). Please refer to Appendix 5.

The assessment of the clinical efficacy of bemcentinib in AML will be made, according to the revised recommendations of the IWG in AML [Cheson, 2003 and Döhner, 2017] as follows:

- Assessment of the % of blasts in a peripheral blood and BM aspirate sample
- Measurement of absolute neutrophil count (ANC)
- Measurement of Platelet count \geq
- Red cell transfusion requirement

The assessment of clinical efficacy of bemcentinib in patients with MDS will be made according to the modified IWG response criteria in myelodysplasia [Cheson, 2006]. Please refer to Appendix 6.

- Assessment of the % of blasts in a peripheral blood and BM aspirate sample
- Measurement of ANC
- Measurement of Platelet count
- Red cell transfusion requirement

BM aspirate and PBMC samples will be analyzed at the designated local laboratory. Wherever possible, an aliquot of BM aspirate will be taken for pharmacodynamic biomarker assessment (see Section 13.5.1).

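### SAP 5.7 gives relapse-free survival two inconsistent start points; read literally, the calculation formula starts the clock before late responders have responded

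*SAP*

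**What the plan says.** The RFS part of SAP 5.7 describes the start of the interval twice. The definition says RFS is "defined as the months from the date of response until the date of relapse". The calculation rule is "Date of disease relapse, patient death, or censoring - Date of first Response evaluation + 1". The first is stated in months and the second in days. Between them stands the population rule: "Relapse Free Survival is defined only for subjects with a best objective response of CR/CRI/CRp/PR for AML patients or CR, PR, MR, PMR for MDS". Non-responders are therefore left out.

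SAP 6.7.1, which reproduces published AML endpoint definitions, gives the starting point of RFS as "Leukemia-free state".

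Protocol 13.4 sets the schedule: "Response assessments will be performed at Cycle 2 Day 1 (pre-dose), Cycle 4 Day 1 and then repeated after every 3 cycles". Protocol 9.3.2 gives the cycle length: "The treatment period will consist of continuous 21-day treatment cycles of bemcentinib". On timing of response, Protocol 12.4 says "it may take longer to observe some clinical responses in some patients", reports that both early and late responses have been seen, and recommends at least three cycles of treatment for that reason.

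**The concern.** A response evaluation is a visit, and a response is one possible finding at it. In plain words, therefore, the first response evaluation is the first time response was looked for, not the first time it was found. A programmer who codes the formula as worded would give every responder the same start, Cycle 2 Day 1, including those who still had active disease then.

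For a late responder, the stretch from that visit to the response is immortal time. A relapse needs a prior response, and a patient who died in that stretch could not have become a responder and entered the analysis. The time can lengthen RFS but never shorten it. The trial is exposed to this because the sponsor reports late responses.

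The rest of the SAP does not resolve the term. SAP 5.15 gives generic Kaplan-Meier code with a duration variable and no derivation. The event-free and overall survival formulas both start at the first bemcentinib intake, which leaves no such doubt.

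**Working it through.** The documents give no numerical RFS figure, so there is nothing to reproduce. The check is date arithmetic on the protocol schedule.

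**Inputs.** Cycle length is 21 days (Protocol 9.3.2). Scheduled assessments are at Cycle 2 Day 1, Cycle 4 Day 1 and every third cycle after that, hence Cycles 7 and 10 (Protocol 13.4; Tables 5 and 6, footnote k).

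**Visit days.** Day 1 of cycle c falls on study day 21 × (c − 1) + 1:
- Cycle 2: 21 × 1 + 1 = Day 22
- Cycle 4: 21 × 3 + 1 = Day 64
- Cycle 7: 21 × 6 + 1 = Day 127
- Cycle 10: 21 × 9 + 1 = Day 190

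**Excess under the literal reading.** This is the day of first documented response minus Day 22. For illustration, suppose relapse is found three cycles (63 days) after response. True RFS by the day-count convention is then 63 + 1 = 64 days for every patient.

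| First response | Excess days | RFS from response | RFS from Day 22 | Ratio |
|---|---|---|---|---|
| Cycle 2 Day 1 | 22 − 22 = 0 | 64 | 64 | 1.00 |
| Cycle 4 Day 1 | 64 − 22 = 42 | 64 | 106 | 1.66 |
| Cycle 7 Day 1 | 127 − 22 = 105 | 64 | 169 | 2.64 |
| Cycle 10 Day 1 | 190 − 22 = 168 | 64 | 232 | 3.62 |

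**Excess under the other reading.** If the term means the first evaluation documenting a response, the start is the date of response and the excess is 0 days in every row.

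**Illustrative effect on the median (literal reading only).** Assume exponential RFS with true median M, and first responses split over Cycles 2, 4 and 7 with shares w and offsets o = 0, 42 and 105 days. Provided the result exceeds 105 days, the median under the formula is M × [1 + log2(Σ w × 2^(o/M))].
- M = 90, equal thirds: Σ = (1 + 1.382 + 2.245)/3 = 1.542; median 146 days (+63%).
- M = 90, split 50/40/10%: Σ = 0.500 + 0.553 + 0.224 = 1.277; median 122 days (+35%).
- M = 180, equal thirds: Σ = (1 + 1.176 + 1.498)/3 = 1.225; median 233 days (+29%).
- M = 180, split 50/40/10%: Σ = 0.500 + 0.470 + 0.150 = 1.120; median 209 days (+16%).

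The splits, the exponential form and both medians are assumptions; none comes from the documents.

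**Scale in a real table.** At the planning response rate of 20%, a cohort of 14 yields 14 × 0.20 = 2.8 responders, and Part B5 yields 20 × 0.20 = 4. SAP 5.7 summarises RFS by mean, median, minimum and maximum. With three responders, one Cycle 7 responder mistimed by 105 days moves the mean by 105/3 = 35 days.

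**The case against.** The strongest reply is that the formula simply restates the definition in looser words. The definition starts at response. The analysis is confined to responders. The appendix starts RFS at attainment of the leukemia-free state. Elsewhere in the RFS text the SAP calls a visit a response assessment, whereas the formula uses evaluation and a capital R, which fits an evaluation at which Response was recorded. Overall survival is handled in the same way: it is defined in months and calculated in days, with differently worded but identical start dates.

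Most of this stands. It makes the harmless meaning the more likely intention. It does not make it the stated rule, because the term stays undefined and its ordinary sense is the other one. The appendix also lists only complete remission for RFS, so it does not itself fix a start date for the partial and marrow responses that SAP 5.7 admits.

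A reader might infer that the SAP definitely builds immortal time into RFS, that the bias affects all responders, or that correcting it will shorten the reported results. The documents do not support any of these. The bias arises under one reading only, it is zero for patients who respond at Cycle 2 Day 1, and if the definition was always going to be followed no result changes. Nothing in the SAP says that the formula overrides the definition.

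The size is also open to challenge. The +63% figure needs a third of first responses to occur at Cycle 7, for which the protocol gives no basis. Optional marrow assessments are allowed at any time and could document a response between scheduled visits, and the ±2-day visit windows are ignored.

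**Conclusion.** The inconsistency is real and should be corrected. SAP 5.7 gives two start points that agree only if an undefined term is read in its less literal sense. Under the literal sense, the excess is 42, 105 or 168 days for first response at Cycle 4, 7 or 10 Day 1, and none at Cycle 2 Day 1. These offsets rest only on the protocol schedule. The +16% to +63% range for the median is illustrative and should not be quoted as an expected bias.

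The consequence is limited. RFS is a descriptive endpoint, tabulated for Part B only. It is not tested and plays no part in the sample size; the hypothesis tests and the sizing concern objective response rate (Protocol 16.5.2 and 16.9). It is nevertheless a listed efficacy endpoint with its own table, curve and listing, and with three or four expected responders per cohort a single mistimed patient would show.

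**What to change.** In the SAP 5.7 formula, replace the start term with *date of the first assessment at which a qualifying response is documented*, where qualifying means the response categories that SAP 5.7 already lists for RFS in AML and in MDS. This matches the definition and the appendix's principle of starting at attainment of response. State RFS in one time unit, or give the conversion from days to months. Apply the same derivation to Table 14.2.2.1, Figure 14.2.2.1.1 and Listing 16.2.6.2.

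The cost is one phrase and a unit statement, with no new data. The wording is right under either reading: if the harmless meaning was intended, no result changes; if not, RFS for late responders becomes shorter by the pre-response time.
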